2.4.2 Planned sample size

The overall sample size for the trial is not fixed. It depends on the number of dose levels being tested.

The 3+3 design does not require sample size specification; the escalation is continued until the maximum administered dose (i.e., a dose with an unacceptable number of DLT) is observed. In total, 26 patients are included in the study.

2.5 Interim analyses

No interim analyses are planned.

3 ANALYSIS POPULATIONS

3.1 Full analysis population (FAP)

The FAP includes all patients who received at least one partial or complete dose of study drug, based on the intent-to-treat principle. The FAP will be used for analyzing efficacy.

Considering that all patients were treated, all analyses will be performed on the safety population (see 3.2).

3.2 Safety population

All patients who received at least one full or partial dose of BAL101553 and had at least one post-baseline safety assessment must be included in the safety analysis populations. The safety analysis population will be used for all safety related analyses (AEs, vital signs, laboratory data, etc.).

Patients will be primarily analyzed according to their originally-assigned dose level.

3.3 PK population

All patients who received at least one full dose of BAL101553 must be included in the PK analysis population.

Protocol deviations that have an impact on the calculation or interpretation of concentrations or PK parameters will be listed in the PK report.

3.4 Maximum tolerated dose-determining population

The MTD-determining population includes all patients from the safety set who meet the following minimum criteria:

- Received at least one dose of BAL101553 and has experienced a DLT;
- Have completed $\geq 80\%$ of their expected dose of BAL101553 for the 6 weeks of combined treatment and 4 weeks of rest (10 weeks total).

Patients who do not meet these minimum evaluation requirements will be regarded as ineligible for the MTD-determining population. These patients will be included in the safety population but will be excluded from the MTD-determining population.

4 STATISTICAL CONSIDERATIONS AND ANALYSIS

4.1 Derived variables

The following derived variables will be applied throughout the study:

- Baseline is defined as the last available assessment prior to first study treatment administration (including unscheduled assessments).
- Adverse event duration (in days, hours or fractions of hours) will be calculated as:
 - ($<\text{event end date.time}>$ minus $<\text{event onset date.time}>$) in days or hours.

If only the date is collected:

- ($<\text{event end date}>$ minus $<\text{event onset date}>$) + 1 in days.

- The following algorithm will be used for the study day determination:
 - Day 1 = Day of first study drug administration (i.e., Day 1). The day before Day 1 is Day -1.
 - Prior to Day 1 the algorithm is ($<\text{visit/examination date}>$ minus $<\text{date of first study drug administration}>$)
 - Day 1 and subsequent days = ($<\text{visit/examination date}>$ minus $<\text{date of first study drug administration}>$) + 1.

- Duration of exposure (in days) will be calculated as: (<date of last study drug administration> minus <date of first study drug administration>) + 1.
- The progression status will be as reported in the case report form (CRF).

4.2 Handling of missing data and/or invalid data and outliers

4.2.1 Missing dates and times

Incomplete/partial dates will be replaced by derived variables and imputed using the following rules:

- If the day of the month is missing, it is imputed to be the 15th if not in the month of treatment. In the event that this leads to inconsistencies with other available data for the patient or if in the month of treatment, the imputation values will be handled case-by-case.
- If both the day and month are missing, they are imputed to be 30 June if not in the year of treatment. In the event that this leads to inconsistencies with other available data for the patient or if in the year of treatment, the imputation values will be handled case-by-case.
- Missing years will be left as missing.
- Missing time will be replaced by '00:00' for start times and '23:59' for end times if time is required.
- Missing minutes will be replaced by '00' for start times and '59' for end times if time is required.

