9.2.1 Adverse Event Characteristics

Definition - An AE is defined as any unfavorable and unintended sign (including an abnormal laboratory finding), symptom or disease temporally associated with the use of a medical treatment (BAL101553 combined with concurrent radiotherapy) or procedure, regardless of whether it is considered to be related to the medical treatment or procedure (attribution of unrelated, unlikely, possible, probable, or definite).

Recording of Adverse Events - ABTC AE Form

- The Investigator will monitor each patient closely for the development of AEs from the time of the first dose of BAL101553 and record all such events on the ABTC AE Case Report Form. Each single sign or symptom must be reported separately.
- **CTCAE term (AE description) and grade:** The descriptions and grading scales found in the revised NCI CTCAE version 4.0 will be utilized for AE reporting until March 31, 2018. CTCAE version 5.0 will be utilized for AE reporting beginning April 1, 2018. All appropriate treatment areas should have access to a copy of the CTCAE version 5.0. A copy of the CTCAE version 5.0 can be downloaded from the CTEP web site (http://ctep.cancer.gov/protocolDevelopment/electronic_applications/ctc.htm). **You must use one of the CTCAE criteria to define your event.**

Adverse events not included in the CTCAE should be reported under "Other" within the appropriate category and graded 1 to 5 according to the general grade definitions - mild, moderate, severe, life-threatening, fatal or disabling - as provided in the CTCAE or the CTCAE Manual. New AEs may be submitted to the CTEP Help Desk at [REDACTED] for annual evaluation by the CTCAE Change Management Committee.

- All AEs should be followed up in accordance with good medical practice. Abnormalities of laboratory events which, in the opinion of the Investigator, constitute AEs (even if not serious) should be followed.
- **Attribution of the AE:** The Investigator will be asked to document his/her opinion of the relationship of the event to study medication as follows:
 - *Unrelated* - The AE is clearly not related to the investigational agent(s).
 - *Unlikely* - The AE is doubtfully related to the investigational agent(s).
 - *Possible* - The AE may be related to the investigational agent(s).

- *Probable* - The AE is most likely related to the investigational agent(s).
- *Definite* - The AE is clearly related to the investigational agent(s).

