5.4.3 Adverse events

Treatment-emergent events are defined as all events occurring after BAL101553 treatment begins. Any adverse event starting prior to the first study drug administration will be reported as medical history. The relationship of an AE to study drug and RT is recorded as unrelated, unlikely, possible, probable, or definite.

For analysis purposes, ‘related to BAL101553’ AEs will be those reported as possible, probable, definite, or those for which the relationship is unknown.

Adverse events will be presented in data listings including dose level, patient, dates/times, study day of event, MedDRA SOC, PT, duration of the event, seriousness, CTCAE grade, intensity, drug adjustment, treatment taken, relationship to study drug, relationship to RT, and outcome.

An overview table (including only treatment-emergent AEs) will also be presented with the number (and percentage) of patients and number of events with:

- Any AE
- Related to BAL101553 AEs
- CTCAE grade 3/4 AEs
- CTCAE grade 3/4 related AEs
- SAEs
- Related SAEs
- AEs leading to dose modifications (i.e., dose reduced or dose interrupted)
- Related AEs leading to dose modifications (i.e., dose reduced or dose interrupted)
- AEs leading to study drug discontinuation
- Related AEs leading to study drug discontinuation
- AEs leading to death
- Related AEs leading to death.

This table will be displayed by dose level.

All treatment-emergent AEs and treatment-emergent AEs related to treatment will be summarized by incidence rate tables broken down by:

- SOC and PT.
- SOC, PT, and worst CTCAE grade.
- SOC, PT, and drug relationship.

Serious treatment-emergent AEs, treatment-emergent AEs leading to dose modifications, leading to study drug discontinuation, or leading to death will be also summarized by SOC and PT. The same analyses will be repeated for related AEs.

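### If treatment emergence is tested on clock times, the SAP's 00:00 rule puts a Day 1 adverse event with no recorded time before the first dose and out of the treatment-emergent tables

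*SAP*

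**What the plan says.** Two SAP sections interact.

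- **Time imputation, SAP 4.2.1.** "Missing time will be replaced by '00:00' for start times and '23:59' for end times if time is required". Partial times follow the same pattern: "Missing minutes will be replaced by '00' for start times and '59' for end times if time is required". Both rules apply only where a time is needed.
- **Treatment emergence, SAP 5.4.3.** "Treatment-emergent events are defined as all events occurring after BAL101553 treatment begins". The next sentence says where other events go: "Any adverse event starting prior to the first study drug administration will be reported as medical history". On the tables, the section says: "An overview table (including only treatment-emergent AEs) will also be presented". The tables by system organ class and preferred term, and those for serious events, dose modification, discontinuation and death, are also built on treatment-emergent events.

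The protocol sets the collection window. Under Protocol 9.2.1 the investigator monitors for adverse events "from the time of the first dose of BAL101553 and record all such events" on the adverse event form.

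**The concern.** For an event dated on the day of first dose, the date alone cannot show whether it came before or after the dose. A programmer who applies SAP 5.4.3 literally may therefore decide that a time is needed, and SAP 4.2.1 then supplies midnight. Midnight is earlier than any dose taken later that day, so the event is classed as pre-dose whatever its true onset.

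Day 1 is the first exposure to both the drug and radiotherapy, and it carries ECGs and serial PK sampling after the dose. Acute symptoms are likely to be noticed then. The error would run one way, towards fewer treatment-emergent events, and safety and tolerability is a stated secondary objective. It would also oppose Protocol 9.2.1, since an event on a form that opens at the first dose is presumably post-dose.

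**Working it through.** The plan states no figure on this point, so there is none to reproduce. The check applies SAP 4.2.1 and then SAP 5.4.3 to an event dated Day 1.

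**Inputs**

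- Missing start time becomes 00:00 and missing start minutes become 00 (SAP 4.2.1).
- Treatment-emergent means after treatment begins; earlier events go to medical history (SAP 5.4.3).
- Clock times are contemplated. SAP 4.1 computes event duration from date and time where available, and the SAP 5.4.3 listing includes dates and times. SAP 4.1 also provides for events with a date only.
- The dose is taken about one hour before each weekday radiotherapy session (Protocol 4.4.1), and both treatments start on the same day (Protocol 4.2). The patient diary has a column for dose time (Protocol Appendix I).
- 26 patients are included (SAP 2.4.2).

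**Step 1: time wholly missing, clock-time test.** The imputed onset is minute 0. The event is prior if 0 < d, where d is the minute of the dose. This is true for every d from 00:01 to 23:59, that is, 1439 of 1439 possible dose minutes.

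**Step 2: only the minutes missing, true onset after the dose in the same clock hour.** With dose minute d and onset minute a, where 0 ≤ d < a ≤ 59, there are 60 × 59 / 2 = 1770 combinations. The imputed onset is on the hour, so the event is prior whenever d > 0. The 59 combinations with d = 0 escape, leaving 1770 − 59 = 1711, and 1711 / 1770 = 96.7%. This weights all minute combinations equally. An onset in a later clock hour than the dose is not affected.

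**Step 3: dose time also missing.** If it is imputed as 00:00 too, the two times tie and the event is not prior.

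**Step 4: date-only test.** The onset date equals the first-dose date and the study day is 1. No event is prior.

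| How the test is run | Day 1 event with no time |
|---|---|
| Clock times, dose time recorded after 00:00 | Placed before the dose |
| Clock times, dose time also missing | Tie, not before the dose |
| Calendar dates only | Not before the dose |

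**Step 5: is there a safeguard?** SAP 4.2.1 has a case-by-case clause: "In the event that this leads to inconsistencies with other available data for the patient or if in the month of treatment". It stands in the bullets for a missing day and for a missing day and month. The bullets for missing times and minutes have no such clause, and no rule holds an imputed onset at or after the dose time.

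**Step 6: weight of one patient.** If one patient's only event of a given kind is removed, incidence at a dose level of n patients falls by 100 / n points: n = 3, 33.3; n = 4, 25.0; n = 5, 20.0; n = 6, 16.7. Over all 26 patients it is 100 / 26 = 3.8. The plan enrols five per dose level, so 20.0 is the natural planning value.

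**The case against.** The strongest reply is that the rule is conditional and SAP 5.4.3 never says that its test needs a time. The SAP's other derivations tied to the first dose, study day and duration of exposure, work on dates, and the SAP foresees events recorded by date alone. The mention of dates and times in SAP 5.4.3 describes a listing, not the classification. The medical-history sentence can also be read as a data-entry convention that matches Protocol 9.2.1, not as an instruction to move records from the adverse event form. All of this stands as a possible reading, and under it nothing is lost. It does not remove the gap, because the SAP does not say which reading applies and the written rules give a wrong result under the other one.

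The limits on impact also stand. The DLT listing in SAP 5.4.1 is not restricted to treatment-emergent events. Serious events from the first dose have their own reporting route (Protocol 9.3.2). The adverse event listing is not expressly restricted either.

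A reader might infer three stronger things that the documents do not support:

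- **Every Day 1 event without a time will be misclassified.** This holds only for a clock-time test with a recorded dose time. The case report form is not among the documents.
- **A number of affected patients can be given.** The documents state neither how many Day 1 events are expected nor how many would lack a time.
- **The partial-date rule adds to the bias.** For a missing day it says "or if in the month of treatment, the imputation values will be handled case-by-case". That guards against mechanical imputation and has no built-in direction of error.

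**Conclusion.** The point holds conditionally. Read together, SAP 4.2.1 and 5.4.3 give a wrong answer for first-dose-day events with a missing time, and usually for those with missing minutes in the same hour as the dose, provided that emergence is tested on clock times and the dose time is recorded. The SAP allows that test and does not exclude it. In the other two cases the effect is nil.

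The number of affected events is unknown and may be zero. Where one patient is affected and it was that patient's only such event, incidence shifts by about 17 to 33 percentage points at a dose level of six to three patients. The consequence is confined to the descriptive treatment-emergent tables and to events dated on one calendar day per patient. The primary endpoint is not directly affected. The change is still worth making, because it corrects a written rule in the direction that is conservative for safety and costs almost nothing.

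**What to change.** Add one sentence to SAP 4.2.1, with a cross-reference in 5.4.3: an adverse event whose onset date equals the date of first dose, and whose time is missing or partial, is treatment-emergent unless the available data show onset before the dose. Keep the 00:00 rule for other uses. The partial-date rules need no change for this purpose.

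The cost is that sentence and one programming condition, best settled before database lock; the SAP was written while the study was ongoing. The downside is that a few symptoms that truly began before the dose on Day 1 may be counted as treatment-emergent.

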4.2.2 Pharmacokinetic data

Treatment of outliers

Individual concentration-time points, if considered anomalous, may be excluded from the analysis at the discretion of the pharmacokineticist following a review of the available documentation. Any such exclusion will be outlined in the PK report.

Entire individual treatment profiles for a subject may be excluded following review of the available documentation. However, results of analysis with and without the excluded profiles may be presented in the PK report. Any such exclusion will be clearly listed in the PK report along with justification for exclusion.

Non-quantifiable concentrations

All concentration values reported as no results (not collected or not determined) values will be treated as missing. For the calculation of concentration summaries, all concentrations below the quantifiable limit (BLQ) will be treated as 0.

For the purpose of calculating PK parameters and plotting mean and individual concentration time profiles, BLQ values will be treated as zero prior to the first measurable concentration. After the first measurable concentration, subsequent BLQ values will be treated as missing.

5 STATISTICAL PLAN AND METHODS

The statistical analysis will be performed using the software package SAS version 9.4 or higher (SAS Institute Inc., Cary, NC 27513, USA). All individual patient data, and results of statistical analyses, will be presented in individual patient data listings and statistical summary tables.

In general, continuous variables will be summarized using the following standard descriptive summary statistics: mean, standard deviation, median, minimum, maximum and number of observations. Categorical data will be described using frequency and percentage. Shift tables will be provided, where appropriate. One additional decimal point will be used for mean, median, Q1, Q3, and two additional decimal points will be used for standard deviation. Percentages will be rounded to one decimal place or more if most results are close to 0 or 100.

Any changes in the planned statistical methods will be documented in the clinical study report.

The following international dictionaries will be used for medical coding:

- Medical History events: MedDRA (version 24.0 or later)
- Adverse events: MedDRA (version 24.0 or later)
- Prior cancer related surgery (MedDRA Version 24.0 or later)
- Prior and concomitant procedures (MedDRA Version 24.0 or later)

Concentration-time profiles of BAL0101553 and BAL27862 will be analyzed by noncompartmental methods and/or nonlinear least squares regression using Phoenix WinNonlin (Build 8.3 or higher; Certara, Princeton, New Jersey, USA). The PK analysis will be reported in a separate report.

5.1 Background characteristics

5.1.1 Patient disposition

Enrollment and disposition data will be presented for each patient in data listings, and summarized by frequency tables. A disposition of patients includes the number and percentage of patients for the following categories: patients who completed the study treatment, patients who discontinued study treatment early with reasons for discontinuation.

Inclusion and exclusion criteria violations and patient enrollment eligibility will be presented by dose level and patient in data listings.

5.1.2 Protocol deviations

Protocol deviations reported during the course of the study will be listed.

Reported protocol deviations will be reviewed prior to database lock.

5.1.3 Demographic and baseline characteristics

Demographic and baseline characteristics of the safety population, including age at baseline, gender, race, ethnicity, height, weight, and disease characteristics, will be summarized by dose level using descriptive statistics or frequency tables, as appropriate. Percentages will be based on the number of patients with available observations in the safety population.

Demographic information and baseline characteristics will be presented in data listings sorted by dose level and patient.

5.1.4 Medical history

Diseases present at baseline as well as previous surgeries will be presented in data listings sorted by dose level and patient.

Medical history data will be summarized by dose level, system organ class (SOC), and preferred term (PT) using the safety population. Prior surgeries characteristics will also be summarized by dose level for the safety population.

5.2 Efficacy analysis

5.2.1 Overall survival

OS is defined as the time from Day 1 dosing to the date of death. Patients who have not died at study closure will be censored at the time of last known alive.

OS will be summarized for the safety population overall. The median time to death, as well as 25th and 75th percentiles, will be determined by Kaplan-Meier method. Its 95% CI will be performed using the Brookmeyer-Crowley method. The associated survival curve will be displayed.

OS will be listed by dose level and patient.

5.2.2 Progression-free survival

PFS is the interval between Day 1 dosing and the earliest date of progression or death due to any cause in the absence of progression. Patients who have not progressed or died at study closure will be censored at the time of their last assessment without progression.

If a patient has no post-baseline progression assessment, the PFS will be censored to 0 days.

PFS will be summarized for the safety population overall. Same statistics and curves than for OS will be displayed.

PFS will be listed by dose level and patient.

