4.2 Treatment Plan

Figure 6 Dose escalation of BAL101553, administered concurrently with RT, given for the first 6 weeks of a 10-week treatment period

Treatment with BAL101553 should begin on the same day as RT.

Patients will receive 6 weeks of concurrent standard RT and BAL101553 treatment. The starting dose of BAL101553 is 4 mg, given orally every day during the 6 weeks of RT. BAL101553 administration and RT must both commence on the same day; this will constitute the first day of the treatment cycle. This period of treatment will be followed by 4 weeks of rest (i.e., no treatment); these 10 weeks will comprise the study treatment.

Patients will be followed by routine blood work, general and neurological examination, Mini-Mental State Examination (MMSE®)²¹, and MRI, and will be monitored for AEs throughout the treatment period. See Section [9.1](#) for schedule.

An MRI will be performed at the end of the 10-week treatment period, after which patients will be off study treatment. All patients will be followed for survival.

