10.2 Off-Study Criteria

Patients will only be off study at the time of death. Patients will be followed every two months for progression, for up to one year from the off-treatment date. All patients will be followed for survival every 2 months for the first 2 years from the off-treatment date; after 2 years, patients will be followed every 6 months until death. Survival status may be obtained by phone call, clinic visit, or medical records (e.g. physician notes/laboratory results of clinic or hospital visit).

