- 20. The MMSE^{®,21} will be performed predose on Day 1 (=baseline) and weekly during RT+BAL101553 treatment when no Neuro Exam is planned (Days 8, 15, 29, 36, 43). Based on the MMSE[®] Score, a Neuro Exam will be scheduled within 1 calendar day if both of the following conditions apply: score < 26 and decline against baseline > 3; see Protocol - Section 5.2.2.

Patients will be followed until death. Patients will only be off study at the time of death. Patients will be followed every two months for progression, for up to one year from the off-treatment date. All patients will be followed for survival every 2 months for the first 2 years; after 2 years, patients will be followed every 6 months until death.

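### Protocol-required progression follow-up ends about week 62, but later deaths without recorded progression count as PFS events at the death date, so the PFS curve beyond about 14 months drifts toward OS

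*SAP*

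**What the plan says.** **Progression follow-up.** Protocol 10.2 states: "Patients will be followed every two months for progression, for up to one year from the off-treatment date". Protocol 4.2.1 and SAP 2.4.1 say the same. On treatment length, Protocol 4.2 counts six weeks of therapy plus four of rest and says "these 10 weeks will comprise the study treatment".

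**Survival follow-up.** This has no end date. Contacts are two-monthly for two years, and SAP 2.4.1 continues: "after 2 years, patients will be followed every 6 months until death". Protocol 10.2 adds: "Survival status may be obtained by phone call, clinic visit, or medical records". Neither document schedules collection of progression at these later contacts.

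**PFS rule.** SAP 5.2.2 runs PFS from Day 1 dosing to "the earliest date of progression or death due to any cause in the absence of progression". On censoring it says: "Patients who have not progressed or died at study closure will be censored at the time of their last assessment without progression". It has no rule for a death that comes long after the last progression assessment. SAP 4.1 takes progression status from the CRF.

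**Outputs.** SAP 5.2.2 says: "Same statistics and curves than for OS will be displayed". Under SAP 5.2.1 these are the Kaplan-Meier median with a 95% CI, the 25th and 75th percentiles, and the curve.

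**The concern.** The two parts of the composite endpoint are observed over different periods. Inside the window both progression and death are captured. After it, only death is required to be captured, yet death still closes the PFS interval at its own date.

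Take two patients who are progression-free at week 62 and both progress at week 70 without its being recorded (weeks chosen for illustration). One dies at week 100, before closure, and gets a PFS time of 100 weeks, 30 weeks too long. The other is alive at closure and is censored at about week 62. Their disease course was the same up to progression, but their handling depends on what happened later.

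Protocol 2.1 says that virtually all of these tumors recur, so unrecorded progression before a late death is a realistic path. Determining PFS is a stated secondary objective, and the upper quartile and the curve are committed outputs.

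**Working it through.** The plan states no expected PFS, so there is no figure of its own to reproduce.

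**1. Where the window ends.** 10 weeks of study treatment + 52 weeks = week 62 from Day 1, or 62 / 4.345 = 14.3 months. It ends earlier for a patient who goes off treatment early.

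**2. When each quartile crosses the window.** SAP 2.4.2 gives 26 patients. With no earlier censoring, the Kaplan-Meier estimate after k events is (26 − k)/26.
- 75th percentile: reached when 6 remain (6/26 = 0.231), not when 7 remain (7/26 = 0.269). It falls beyond week 62 only if at least 7 of 26 are progression-free then.
- Median: needs at least 14 of 26 (13/26 = 0.50 already reaches it).
- 25th percentile: needs at least 20 of 26 (20/26 = 0.769; 19/26 = 0.731).

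**3. The only progression rate in the documents.** Protocol 4.1 gives about 20% in the first 10 weeks. If this is assumed constant from Day 1:
- hazard = −ln(0.8)/10 = 0.0223 per week
- median = ln 2 / 0.0223 = 31.1 weeks; 75th percentile = ln 4 / 0.0223 = 62.1 weeks
- S(62) = exp(−0.0223 × 62) = 0.251, so 26 × 0.251 = 6.5 patients expected progression-free

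The expected 75th percentile therefore sits on the edge of the window.

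**4. Range over assumed medians m.** Exponential PFS, S(62) = 0.5^(62/m). The third column is the binomial probability of 7 or more out of 26. The last column is the share of simulated trials of 26 in which the SAP rule alters the 75th percentile, compared with following progression throughout.

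| Assumed median PFS (weeks) | S(62) | P(7 or more of 26) | Simulated share altered |
|---|---|---|---|
| 20 | 0.12 | 2.6% | 2–3% |
| 26 | 0.19 | 22% | 20–24% |
| 31.1 | 0.25 | 49% | about 50% |
| 40 | 0.34 | 84% | about 82% |

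At a 31.1-week median, the chance that the median itself falls beyond the window (14 or more of 26) is about 0.2%.

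**5. Time origin.** Protocol 4.1 times the 20% from initial diagnosis; SAP 5.2.2 starts PFS at Day 1. Suppose Day 1 is 3 to 4 weeks after diagnosis with no progression in between (an assumption). Then 20% progress in 7 or 6 weeks:
- hazard = −ln(0.8)/7 = 0.0319 or −ln(0.8)/6 = 0.0372 per week
- median = 21.7 or 18.6 weeks; 75th percentile = 43.5 or 37.3 weeks, inside the window
- S(62) = 14% or 10%

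**6. Size when it happens.** Assume median survival after progression of 6 to 12 months and closure 120 to 200 weeks after Day 1; neither is in the documents. When the 75th percentile falls beyond the window, it is typically 2 to 4 months later than with full progression follow-up.

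**The case against.** The strongest reply is that little depends on this. The primary endpoint is DLT for the MTD. PFS is descriptive, pooled over dose levels and untested. Counting death from any cause is conventional, and a death with no prior progression is dated correctly. OS and PFS are both listed by patient, so a late PFS time equal to OS can be seen. With 26 patients, sampling variation in the 75th percentile is far larger than the distortion: about 37 to 99 weeks in simulation at a 31-week median. All of this stands and limits the weight of the point. It does not remove the inconsistency in how late patients are handled.

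A reader might infer more than the documents support:

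- *That the reported 75th percentile is unreliable in general.* It is affected only if roughly a quarter or more of patients are progression-free at week 62. The documents' one rate puts that near an even chance on one reading of its time origin and makes it unlikely on the other.
- *That every late PFS time is overstated.* Only those with an unrecorded earlier progression are.
- *That nothing but deaths can enter the curve after week 62.* Later progression is not required to be collected. That does not show it is absent: the CRF is not in the documents, standard-of-care follow-up continues (Protocol 4.1), and SAP 5.2.2 does not restrict progression dates to scheduled visits.

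**Conclusion.** The mismatch is in the text, and applying SAP 5.2.2 as written makes PFS beyond about 14 months drift toward OS. The 25th percentile is unaffected and the median almost always so.

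For the 75th percentile, the chance of an effect runs from about 2–3% at an assumed 20-week median, through about 50% at 31 weeks, to about 82% at 40 weeks. The 40-week case has no support in the documents and only shows the range. These figures assume exponential PFS, 26 patients, and no progression recorded after the window; any later progression that does reach the CRF reduces the effect. The size of a shift also depends on the closure date and on survival after progression, neither of which is given.

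This is a modest but certain defect in a descriptive secondary output. It is worth correcting because the correction is cheap.

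**What to change.** **(a) Preferred.** Amend Protocol 4.2.1 and 10.2 and SAP 2.4.1 so that the date of first progression, where known from clinic or medical records, is recorded at the survival contacts already scheduled, until progression or death. This treats the cause and keeps the 75th percentile estimable. The cost is a protocol change and a small addition to data collection. Dates obtained this way are less standardised than RANO assessments. SAP 2.4.2 already counts 26 patients, so for some of them the dates may have to be taken from records after the event.

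**(b) In addition, or where (a) is not feasible for patients already past the window.** Add to SAP 5.2.2 a sensitivity analysis that censors at the last progression assessment when death comes more than two scheduled intervals (4 months) after it. State there that the primary PFS curve beyond about 14 months is not informative for progression. The cost is a few lines of SAP text and one more analysis. Its 75th percentile may be not estimable: in simulation this happened in roughly 27–36% of runs at a 31-week median. For that reason it is proposed as a sensitivity analysis and not as the primary rule.
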